Document Cover Page

Official Title of the Study: A randomized clinical trial of single dose liposomal bupivacaine delivered via VATS intercostal nerve block vs continuous bupivacaine infusion delivered via indwelling subscapular analgesic catheter in patients undergoing surgical stabilization of rib fractures

NCT Number: NCT03305666

Date of Document: April 27, 2017

COMIRB Protocol

COLORADO MULTIPLE INSTITUTIONAL REVIEW BOARD
[name] [contact] [contact]

Protocol #: 17-0685

Project Title: A randomized clinical trial of single dose liposomal bupivacaine delivered via VATS intercostal nerve block vs continuous bupivacaine infusion delivered via indwelling subscapular analgesic catheter in patients undergoing surgical stabilization of rib fractures

Principal Investigator: [name] MD

Version Date: V1 4/27/2017

I. Hypotheses and Specific Aims:

The hypothesis of this clinical trial is that among patients undergoing surgical stabilization of rib fractures (SSRF), liposomal bupivacaine delivered via VATS intercostal nerve block provides comparable analgesia to the pain catheter, as measured by both pulmonary function and narcotic use.

II. Background and Significance:

Rib fractures represent a common injury pattern with high associated morbidity and mortality (1). Effective pain control in both the acute and long term periods remains a challenge (2). Surgical stabilization of rib fractures (SSRF) is now a recommended treatment for patients with severe chest wall injuries (3-5). In addition to stabilization of the chest wall, SSRF offers a unique opportunity to deliver directed, loco-regional anesthesia. Loco-regional anesthesia is a recognized, essential component of multi-modal anesthesia for patients with rib fractures in order to both decrease pain and minimize the use of opioids and their associated side effects (6, 7).

Delivery options for loco-regional anesthesia to patients with rib fractures share in common the intention of anesthetizing the intercostal nerves. Moving from the spinal cord distally, modalities include thoracic epidural catheters, paravertebral blocks or catheters, and rib blocks. Although rib blocks may be accomplished via a variety of techniques, the two most common intra-operative techniques are video-assisted thoracoscopic surgery (VATS) intercostal nerve blocks [Figure 1] and indwelling, subscapular catheters (Figure 2).

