In general, neuraxial modalities such as thoracic epidural and para-vertebral injections/catheters are subject to a wide array of limitations, including patient coagulopathy (Internal Normalized Ratio > 1.5), co-existing spine fractures, peri-insertion and removal holding of venous thromboembolism pharmacoprophylaxis, and provider availability. For these reasons, our current practice is to insert a subscapular “pain catheter” at the conclusion of the SSRF operation (Figure 2); this catheter provides a continuous infusion of 0.25% bupivacaine and may be left in place for several days.

Although favorable results using the pain catheter have been published in patients with rib fractures who have not undergone SSRF (8), we have noticed several limitations to this treatment modality. First, position is highly variable; and, because the catheter is not truly in the space of the intercostal nerves (Figure 3), drug delivery is likely irregular. This variability may be particularly relevant in obese patients; and the median body mass index of patient who underwent SSRF at Denver Health is 29 kg/m². Beyond catheter placement, we have also experienced issues with leakage of drug from the skin entry site of the catheter. Moreover, catheters frequently become dislodged or inadvertently removed during patient transport. Further, the indwelling foreign body likely introduces some risk of infection. Finally, the presence of the catheter is distressing to many patients.

Liposomal bupivacaine (Exparel, Pacira Pharmaceuticals, Inc., Parsippany, NJ, www.pacira.com) provides sustained analgesia for up to 72 hours following a single injection of the drug delivery system. The safety and efficacy of liposomal bupivacaine has been evaluated

in over 1,300 subjects and 21 clinical trials (refs from pamphlet). Although many of these trials have included thoracic surgery patients (9-11), no trial has evaluated the efficacy and safety of liposomal bupivacaine administered to patients with rib fractures undergoing SSRF. Potential benefits as compared to current practice include directed injection into the intercostal nerve space using a VATS approach, as well as obviation of the need for an indwelling catheter. The hypothesis of the current clinical trial is that, among patients undergoing SSRF, liposomal bupivacaine delivered via VATS intercostal nerve block provides comparable analgesia to the pain catheter, as measured by both pulmonary function and narcotic use.

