III. Preliminary Studies/Progress Report:

Although SSRF is now a recognized treatment for patients with severe chest wall injuries, the method of loco-regional anesthesia is less standardized. Currently thoracic epidural and paravertebral catheters are both common methods for delivering loco-regional anesthesia. Thoracic epidural catheters offer the benefit of bilateral analgesia and have been shown to reduce the length of mechanical ventilation (3). Unfortunately they are contra-indicated in the setting of spine fractures and mild coagulopathy, and may require the addition of a consultative service to manage. Paravertebral pain catheters have equivalent pain control to epidural catheters, but can be used in patients with spine fractures and can be placed surgically or by emergency teams using anatomic landmarks or ultrasound guidance (3). Denver health has found that these catheters are not without issues for our patients. Some issues that we have personally experienced include drug leakage, dislodgement, and irregular drug delivery. Other pain loco-regional analgesic modalities such as intrapleural pain catheters, transcutaneous patches, transcutaneous electrical nerve stimulation, and acupuncture have limited evidence to support their use (3). While still a relatively new technique for loco-regional anesthesia, liposomal bupivacaine has shown favorable results in patients undergoing thoracoscopies and thoracotomies, resulting in shorter hospital length of stay (11) and statistically significant additional analgesics (10). The ease of delivery of liposomal bupivacaine and the ability to avoid bothersome catheters may make it the optimal method for loco-regional anesthesia in patients undergoing SSRF.

IV. Research Methods

A. Outcome Measure(s):

Individuals undergoing SSRF will be randomized to two treatment arms. Primary outcomes will be pulmonary function and narcotic requirement by each subject.

Pulmonary function will be measured using the Standardized Assessment of Respiratory Function (SCARF) score, measured at 10 am daily. This scale has 4 components, and one point award for each of the following:

- 1) Numeric Pain score >4 (on the 10 point pain scale)
- 2) Incentive spirometry <50% predicted
- 3) Poor cough
- 4) Respiratory rate ≥ 20

Daily Narcotic use will be measured using equi-analgesic doses as shown in the table below.

Narcotic	Dose	Unit	Route
Hydromorphone	1.5	Mg	IV
Hydromorphone	7.5	Mg	PO
Fentanyl	100	Mcg	IV
Morphine	10	Mg	IV

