Morphine	30	Mg	PO
Oxycodone (Percocet)	20	Mg	PO
Hydrocodone (Vicodin)	30	Mg	PO

B. Description of Population to be Enrolled:

Adults undergoing surgical stabilization for rib fractures are eligible for this clinical trial. Any individuals that are pregnant, incarcerated, less than 18 years old, or have a known allergy or hypersensitivity to bupivacaine will not be eligible for enrollment.

C. Study Design and Research Methods

This is a non-inferiority, randomized clinical trial that compares two different delivery options for loco-regional anesthesia for patients undergoing surgical stabilization of rib fractures. Randomization will be accomplished using a standard function in Microsoft Excel that randomly chooses either the number 0 or 1.

Prior to patient's SSRF procedure they will be localized to one of two study arms:

- 1) Pain Catheter: placed in the subscapular space at the time of surgery and results in a continuous infusion of 12ml/hr of 0.25 bupivacaine and is left in place for a maximum of 120 hours.
- 2) Single injection liposomal bupivacaine: a mixture of 20mL liposomal bupivacaine, 20 mL 0.25% bupivacaine, and 10mL sterile saline (50mL total) that is delivered into the intercostal space during VATS using a 22 gauge needle directed at ribs 3 through 8. (178mm????)

The SSRF procedure will be standardized for all patients to include: 1) flexible bronchoscopy, 2) E-Z Blocker bronchial blocker (figure 5), and 3) VATS evacuation/irrigation of the pleural space.

Postoperatively, standard multimodal analgesia will be used in all patients (barring any contra-indications) to include: 1) Acetominophen 650 mg PO q6H, 2) Ibuprophen 800 mg PO q6h, and 3) Gabapentin 300 mg PO TID

Subjects will be followed for 28 days or until discharged from the hospital, whichever comes first. Crossover from one study arm to the other will not be permitted. Patients in whom pain is not well controlled postoperatively will be given additional analgesics other than bupivacaine.

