Inferiority of liposomal bupivacaine as compared to pain catheter will be defined as median daily SCARF score one point higher. Standard deviation of the SCARF score among patients with rib fractures in Denver Health surgical intensive care unit is 1.1. Using beta = 0.80 and alpha = .05, this returns a total sample size of 34 subjects. Twenty-four SSRF procedures are performed annually at Denver Health, thus we conclude that the trial is feasible and may be completed in 1.5 years.

A standard data collection tool will be used (see Data Collection Tool). All statistical analysis will be conducted using SAS version 9.4 (SAS Inc., Carey, NC). Statistical significance will be defined as $p < .05$. The distribution of continuous variable will be accessed for normality using the Kolmogorov-Smirnov test. Normally distributed continuous variables will be compared using the student's t-test. Non-normally distributed variables will be compared using the Wilcoxon Rank test. Categorical variables will be compared using chi-squared test, unless expected cell counts were <10 , in which case Fischer's exact test will be used.

G. Summarize Knowledge to be Gained:

Rib fractures are common and associated with both acute and chronic pain. This trial will compare two loco-regional treatment modalities currently in use at Denver health to determine the optimal method to decrease post-operative pain and minimize opioid use. Denver Health is a leader in trauma care, including rib fractures. Our team has been produced multiple peer reviewed studies detailing current recommendations for treatment of rib fractures. We will continue to explore novel approaches for trauma patients suffering from rib fracture pain control to further improve patient outcomes and patient satisfaction.

H. References:

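### The days behind the primary SCARF median are not defined; a whole-stay median could favour non-inferiority if stays pass day 5 and any deficit fades after treatment

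*Combined protocol and SAP*

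**What the plan says.** Section IV.A makes pulmonary function (the SCARF score) and narcotic requirement the primary outcomes, both attached to the individual subject. SCARF is "measured at 10 am daily", with no first or last day. Section IV.F sets the margin: "Inferiority of liposomal bupivacaine as compared to pain catheter will be defined as median daily SCARF score one point higher". It then gives the variability, "Standard deviation of the SCARF score among patients with rib fractures in Denver Health surgical intensive care unit is 1.1", and a total of 34 subjects. The tests named are generic two-group ones (t-test or Wilcoxon). No day, window or repeated-measures method is given.

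The only period in the plan is in section IV.C: "Subjects will be followed for 28 days or until discharged from the hospital, whichever comes first". This is a follow-up period, not an analysis window.

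The treatments are shorter. Section II says that liposomal bupivacaine "provides sustained analgesia for up to 72 hours following a single injection", and section IV.C says that the catheter "is left in place for a maximum of 120 hours". Section I states the hypothesis that the injection "provides comparable analgesia to the pain catheter, as measured by both pulmonary function and narcotic use". Section IV.E states that the trial is not blinded to providers, patients or the coordinator who collects the data.

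**The concern.** The 1-point margin has a definite meaning only once the days are fixed. A median over days 1-5 compares patients while at least one treatment may be acting. A median over the whole stay can also include days when neither is. In a non-inferiority trial, adding days on which the arms no longer differ shrinks the estimated difference and makes a pass easier.

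Two things are at stake. A real 1-point deficit during treatment could be diluted below the margin. And because the days are open in an unblinded trial, the choice could be made after the results by arm are known.

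**Working it through.** **The plan's own figure.** Inputs from section IV.F: margin 1, SD 1.1, alpha 0.05, and power 0.80 (printed as beta). I assume 1:1 allocation and no true difference. The normal formula at one-sided 5% is n per arm = 2 × (1.645 + 0.842)² × 1.1² / 1² = 14.96, so 15 per arm, 30 in total. The t distribution needs 16 per arm (32). Dividing by the Wilcoxon efficiency 3/π gives 16 / 0.955 = 16.8, so 17 per arm, which is the stated 34. At 17 per arm the t-test has power 0.829. The sample size is not in dispute, and a one-sided 5% test is consistent with it.

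**Dilution by hand.** Suppose the liposomal arm is exactly 1 point worse on days 1-5 and equal afterwards, and every patient stays L days (5 or more). A per-patient mean over the stay then differs by 5/L. Take 1.1 as the SD of that summary. The standard error is 1.1 × √(2/17) = 0.377, and the chance of passing is Φ((1 − 5/L)/0.377 − 1.645):
- L = 5: difference 1.00, chance 0.05
- L = 7: difference 0.71, chance 0.19
- L = 10: difference 0.50, chance 0.38

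**Simulation of the per-patient median.** Assumed, because the documents do not give them: lognormal stay (log-SD 0.5, 1 to 28 days), within-patient correlation 0.5, normal scores, deficit on days 1-5 only, and a pass when the one-sided 95% upper t-bound is below 1. There are 17 per arm, and SD 1.1 is taken as the SD of a single daily score. A *false pass* is a pass when the days 1-5 difference is exactly 1 point.

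| Median stay (days) | 4 | 5 | 6 | 8 | 10 |
|---|---|---|---|---|---|
| Whole-stay median, false pass | 8% | 12% | 17% | 30% | 45% |
| Days 1-5 median, false pass | 5% | 5% | 5% | 5% | 5% |

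At median stays of 6, 8 and 10 days the whole-stay difference falls to about 0.78, 0.66 and 0.55.

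**Sensitivity of the whole-stay median, at median stays of 6 / 8 / 10 days.**
- SD 1.1 taken as the SD of the per-patient summary: 14% / 22% / 31%.
- Correlation 0.3: 19% / 38% / 55%. Correlation 0.7: 14% / 26% / 38%.
- Scores rounded to 0-4 (assumed mean 1.5): 18% / 30% / 44%; the days 1-5 median then gives about 5-6%.
- Half the deficit persists after day 5: 10% / 14% / 19%.
- The whole deficit persists, or all stays are 5 days or less: about 5%, so no bias.

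**The case against.** The strongest reply has four parts.

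*The level of summary is less open than it looks.* Section IV.A attaches the primary outcomes to each subject, section IV.F counts subjects, and two-sample tests need independent observations. Together these point to one value per patient. A reader might infer that a median over pooled patient-days is equally open; the text gives it little support. This part stands, but it does not settle the days.

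*The bias is conditional.* A reader might infer that the plan will favour non-inferiority. The documents do not support that: they give no length of stay and no time course for any deficit, and they do not say that the whole stay will be analysed. *Could favour* is as far as the text goes.

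*Whole-stay recovery may be the target.* If so, the smaller difference is the quantity of interest and nothing passes falsely. I read comparable analgesia as an effect during treatment, but the plan does not say so. It should state which is meant.

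*The Data Collection Tool is not in the supplied text.* It is cited in section IV.F and may limit the days recorded. This stands as a caveat, although a list of recorded days would not by itself define the summary.

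It is also tempting to infer from the agreement with 34 subjects that SD 1.1 describes a per-patient summary. That would be circular: 1.1 went into the formula whatever it describes, so the sample size cannot show which it is.

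**Conclusion.** The gap is real and sits in the only non-inferiority criterion: the days entering the SCARF median are not stated, and one value per patient is implied rather than specified. It should be fixed.

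The direction of any bias is towards non-inferiority under a whole-stay median, provided that stays run past day 5 and the deficit fades. Its size cannot be determined from the documents. Under the stated assumptions false passes range from about 8% at a median stay of 4 days to about 45% at 10 days, against a nominal 5%. They return to 5% if the deficit persists in full or if no stay exceeds 5 days. These figures also rest on an on-treatment target and a one-sided 95% bound, neither of which the plan states. Confidence is high that the definition is missing from the supplied text and moderate that it matters in practice.

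**What to change.** Before any outcome data are examined, amend section IV.F as follows:

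1. Define the primary SCARF value as one value per patient: the median of the 10 am scores over postoperative days 1-5, or to discharge if earlier.
2. Compare the arms by a one-sided 95% confidence bound against the 1-point margin.
3. Use the same window for daily narcotic use.
4. Report days 1-3, days 4-5 and later days descriptively, without separate margin tests. Requiring all of days 1-5, 1-3 and 4-5 to pass would cut the chance of passing with no true difference to about 81-87% (daily SD).
5. State whether SD 1.1 is for a single daily score or a per-patient summary, from its source data.

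If whole-stay recovery is the intended target, say so and justify the margin for it.

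**Cost.** Wording only and no added patients, provided the Data Collection Tool records SCARF through day 5; otherwise that form changes too. With no true difference, the days 1-5 median passes about 94% of the time against 95-96% for the whole-stay median (daily SD), or about 83% against 82-83% (summary SD).

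**Downsides.** Scores after day 5 leave the primary result. A days 1-5 median can still miss a deficit confined to days 4-5: it then passes about 64-72% of the time with daily SD, or 48-56% with summary SD. The days 4-5 description covers only patients still in hospital.

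### The one-point SCARF margin has no stated rationale, catheter effect or confidence-bound rule behind it, so a pass cannot support a claim of comparable analgesia

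*Combined protocol and SAP*

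**What the plan says.** Section IV.C describes the design: "This is a non-inferiority, randomized clinical trial that compares two different delivery options for loco-regional anesthesia". Section IV.F gives the margin: "Inferiority of liposomal bupivacaine as compared to pain catheter will be defined as median daily SCARF score one point higher". Section IV.A defines the score: "This scale has 4 components, and one point award for each of the following". The range is therefore 0 to 4, with higher scores worse.

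The size calculation in IV.F rests on two sentences: "Standard deviation of the SCARF score among patients with rib fractures in Denver Health surgical intensive care unit is 1.1" and "Using beta = 0.80 and alpha = .05, this returns a total sample size of 34 subjects". The rest of IV.F names ordinary t and Wilcoxon comparisons at p < .05. It gives no confidence-bound rule for the margin.

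The conclusion sought in sections I and II is that "liposomal bupivacaine delivered via VATS intercostal nerve block provides comparable analgesia to the pain catheter", judged on both pulmonary function and narcotic use. Narcotic use has no margin. On the catheter's own benefit, section II says only that "favorable results using the pain catheter have been published in patients with rib fractures who have not undergone SSRF". The documents give no figure for the catheter against no block, on SCARF or any other scale.

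**The concern.** A non-inferiority margin limits how much of the control's benefit may be lost. To choose it, one needs either an estimate of that benefit or a clinical argument that a loss of this size does not matter. The plan offers neither for one point.

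Three features of the trial make the gap harder to ignore. The cited support for the catheter comes from patients without surgical stabilization, whereas everyone here is stabilized. Both arms receive multimodal analgesia, and uncontrolled pain is treated with further analgesics (IV.C), which can narrow any SCARF difference between arms. Section II itself expects uneven drug delivery from the catheter.

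At stake is the wording of the conclusion. A moderately worse block could meet the criterion and be reported as comparable to the catheter. The other primary outcome sets no numeric limit that would stop this.

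**Working it through.** **Inputs.** From IV.F: margin 1 point, SD 1.1, alpha .05, power 0.80 (the plan calls it beta), total 34. From IV.A: four one-point items. Assumed: 17 per arm (IV.C randomizes by a simple 0/1 draw and states no ratio), normal theory on means, and SD 1.1 applying to the quantity analysed.

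**The plan's own figure.** With no true difference, the normal approximation gives n per arm = 2 × [1.1 × (z for alpha + z for power) / 1]².
- One-sided .05: 2 × [1.1 × (1.645 + 0.842)]² = 14.96, so 15 per arm and 30 in total. The t-test needs 32. Dividing its 16 per arm by the Wilcoxon efficiency of 0.955 gives 16.75, so 17 per arm and 34 in total.
- One-sided .025: 38 by the normal approximation and 42 by the t-test.

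The stated 34 therefore fits a one-sided .05 reading, and the size calculation is not the problem.

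**Size of the margin.** 1/4 = 25% of the scale; 1/1.1 = 0.91 SD.

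**What a correct test of this margin lets through.** SE = 1.1 × √(2/17) = 0.377, df = 32. The test passes if the observed difference (injection minus catheter) plus t × SE is below 1.0. The largest observed difference that passes is:
- one-sided .05: 1 − 1.694 × 0.377 = 0.36
- one-sided .025: 1 − 2.037 × 0.377 = 0.23

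For a true harm d, the pass probability comes from the noncentral t distribution with noncentrality (1 − d)/0.377 in absolute value. The last column is the normal probability that the observed difference is below one point, Φ((1 − d)/0.377), with no confidence bound.

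| True harm (points) | One-sided .05 | One-sided .025 | Observed difference only |
|---|---|---|---|
| 0 | 83% | 73% | >99% |
| 0.25 | 62% | 49% | 98% |
| 0.5 | 36% | 25% | 91% |
| 0.75 | 16% | 9% | 75% |
| 1.0 | 5% | 2.5% | 50% |

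**Link to the catheter's effect.** An injection that keeps none of the catheter's benefit is worse by exactly that benefit. The harm column can therefore also be read as the catheter's unknown effect. Below one point, such an injection lies inside the margin; at one point or more, a correct test passes it at most 5% (or 2.5%) of the time. The documents do not say which case applies.

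**Price of a tighter margin (illustrative only).** For a mean of three daily scores, SD = 1.1 × √((1 + 2r)/3). Taking within-patient correlation r from 0.3 to 0.7 gives SD 0.80 to 0.98. At 17 per arm and one-sided .05, power is 97% to 90% for a margin of 1.0 and 85% to 70% for 0.75. That is a loss of about 13 to 19 percentage points.

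**The case against.** A reader might infer that a much worse, or even inert, injection would readily be declared comparable. The documents do not support that. Under a correct test the observed difference must be 0.36 or less, and true harms of 0.75 and 1.0 points pass only 16% and 5% of the time. The inert case depends on a catheter effect below one point, which the documents neither show nor exclude. An inert injection passes often only where the catheter adds little. The mixture also contains active drug, and section II describes analgesia lasting up to 72 hours. This objection stands, and the point is limited accordingly.

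One point is also the smallest step that an individual score can take, so the 25% partly reflects a coarse scale. Section II lists catheter drawbacks (leakage, dislodgement, infection risk, distress) that could justify accepting some loss of analgesia. These explain why a non-inferiority design was chosen, but they do not derive a margin of one point.

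Narcotic use is a second primary outcome, and a failing block might show there because extra analgesics are given. That is fair, but without a margin it sets no limit on what may be called comparable.

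Finally, any tighter threshold, such as 0.5 or 0.75, would be as unanchored as one point and would cost power. This also stands, so no tighter margin is asked for.

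**Conclusion.** The point holds as a mismatch between margin and claim. One point is a quarter of the scale and 0.91 SD, with no rationale, no stated catheter effect and no confidence-bound rule. Meeting it cannot establish comparable analgesia.

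The exposure is to moderate harm: a true 0.5-point deficit passes 36% of the time at one-sided .05 and 25% at .025. If the sentence in IV.F is read as a comparison of the observed difference with one point, the figure is 91%. That last number reflects the missing rule; the mismatch with the claim would remain under a correct test.

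These figures assume 17 per arm, no dropout, SD 1.1 and normal theory on means. They are approximate for a 0-4 score, and the SD comes from intensive-care rib-fracture patients, not specifically from those having stabilization. If the SD of the analysed summary is below 1.1, the margin exceeds 0.91 SD.

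**What to change.** Keep 34 subjects and amend IV.F as follows:

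1. Declare non-inferiority only if the upper confidence bound for the SCARF difference (injection minus catheter) is below 1.0. Name the confidence level and the SCARF summary to which it applies. At 17 per arm, power is 83% at one-sided .05 and 73% at .025.
2. Report the interval whatever the result.
3. Word a positive result as not worse by one SCARF point, and bring sections I and II into line by removing the comparable-analgesia claim.
4. State that, without a known catheter effect over no block, the trial cannot show that either block is better than none.

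This takes a few sentences and no new patients or data. The downside is a less favourable claim. Tightening the margin is a separate trade-off and is not needed for this fix.

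### The normality pre-test on the 0–4 SCARF score reacts mainly to the scale's steps, leaves the primary test open to unstated choices, and usually ends in a rank p-value with no estimate to hold against the one-point margin

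*Combined protocol and SAP*

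**What the plan says.** Section IV.A makes SCARF and narcotic use the primary outcomes. On SCARF it says: "This scale has 4 components, and one point award for each of the following". A single reading is therefore an integer from 0 to 4. It is taken daily, and no rule reduces the daily readings to one value per patient.

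Section IV.F gives the only analysis rule. "The distribution of continuous variable will be accessed for normality using the Kolmogorov-Smirnov test". Variables found normal go to Student's t-test. For the rest: "Non-normally distributed variables will be compared using the Wilcoxon Rank test". Categorical variables go to chi-squared or Fisher's exact test. The section does not say:

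- whether SCARF counts as continuous;
- whether the pre-test is run on the pooled sample or by arm;
- which Kolmogorov-Smirnov critical values apply.

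The design is non-inferiority (section IV.C), and the margin is in SCARF points: "Inferiority of liposomal bupivacaine as compared to pain catheter will be defined as median daily SCARF score one point higher". The sample size rests on an SD: "Standard deviation of the SCARF score among patients with rib fractures in Denver Health surgical intensive care unit is 1.1". It then states: "Using beta = 0.80 and alpha = .05, this returns a total sample size of 34 subjects". No test and no sidedness is named for that calculation.

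**The concern.** The Kolmogorov-Smirnov test assumes a continuous variable. On a five-value score it can reject because of the jumps in the distribution alone, even when the underlying severity is exactly normal. The result then says little about whether a t-test would be sound, yet it decides how a primary outcome is analysed.

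Three things are at stake. The first is whether the primary test is really fixed in advance, which matters more because section IV.E says the trial is unblinded. The second is whether the selected test yields something that can be set against a margin of one SCARF point. The third is whether the choice of branch can change the verdict.

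**Working it through.** **Inputs.** Margin 1 point, SD 1.1, alpha .05, power .80 (written as beta) and N = 34, all from section IV.F; the 0–4 integer scale from section IV.A. Assumed, because the plan gives none of them: 17 per arm (section IV.C describes simple 0/1 randomization), no dropout, independent patients, and the shapes of the score.

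**Reproducing N = 34.** With n per arm = 2·SD²·(z₁₋α + z₀.₈)² / margin²:

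- One-sided .05: 2 × 1.21 × (1.645 + 0.842)² = 14.96, so 15 per arm, N = 30.
- Two-sided .05: 2 × 1.21 × (1.960 + 0.842)² = 18.99, so 19 per arm, N = 38.
- One-sided .05, noncentral t: 15.68, so 16 per arm, N = 32.
- The same with the usual Wilcoxon allowance: 15.68 × π/3 = 16.42, so 17 per arm, N = 34.
- Two-sided noncentral t, with or without that allowance: 21 per arm, N = 42.

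A one-sided t calculation comes within two patients of 34, and a one-sided Wilcoxon calculation gives it exactly. The stated figure does not show which test was meant.

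**Why the steps drive the pre-test.** The statistic D is the largest gap between the empirical distribution and a normal curve with the sample mean and SD. At a value held by a share p of the sample, the empirical distribution jumps by p, so D is at least p/2. The simulated 5% critical values, corrected for the estimated mean and SD, are about 0.149 at n = 34 and 0.207 at n = 17. Pooled, rejection is certain once one score is shared by more than 2 × 0.149 × 34 = 10.1 patients, that is 11 of 34. On a five-value scale with SD near 1.1 that is ordinary. The uncorrected critical value at n = 34 is 0.227, and the same bound then needs 2 × 0.227 × 34 = 15.4, that is 16 of 34.

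**How often it rejects (simulation).**

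| SCARF summary and version of the test | Rejects normality |
|---|---|
| One-day score, corrected, pooled (n = 34) | 97–100% |
| One-day score, corrected, either arm, SD near 1.1 | about 88–99.7% |
| One-day score, corrected, one given arm | 53–93% |
| Per-patient median, corrected, pooled | about 100% |
| Per-patient median, corrected, one given arm | 79–97% |
| Per-patient mean of 3–7 days, corrected | 8–64% pooled; 5–27% in one arm |
| One-day score, uncorrected, pooled | 13–82% |
| One-day score, uncorrected, either arm, rounded-normal scores | 7–23% |

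The multi-day rows assume a within-patient correlation of 0.3–0.7. A flat distribution with SD 1.41, well above the plan's 1.1, brings the corrected either-arm rate down to 77%. The top of the uncorrected pooled range comes from floor-skewed scores.

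**Power of the two branches.** The plan does not say how the margin enters either test. Here 1 was subtracted from each injection-arm score. True difference 0, 17 per arm, one-sided .05; score probabilities are listed for 0 to 4:

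| Shape of the 0–4 score | SD | t | Wilcoxon |
|---|---|---|---|
| Rounded normal, underlying mean 1.0 | 1.01 | 88% | 87% |
| Rounded normal, underlying mean 1.5 | 1.09 | 83% | 80% |
| Rounded normal, underlying mean 2.0 | 1.11 | 82% | 78% |
| .35/.35/.15/.10/.05 | 1.15 | 79% | 83% |
| .40/.30/.15/.10/.05 | 1.18 | 78% | 82% |
| .50/.20/.15/.10/.05 | 1.22 | 75–76% | 82–83% |

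The sign of the difference follows the shape. Over all shapes tried with SD close to 1.1, Wilcoxon power was roughly 76–87%. A wider symmetric shape (SD 1.20) lowers both, to 76% by t-test and 71% by Wilcoxon. Both tests held their error rate at or below about 5% when the true mean difference was one point.

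**Disagreement.** One test declared non-inferiority and the other did not in about 3–9% of trials. The low end is the first row of the table and the high end is the last.

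**Narcotic use.** With lognormal data (log SD 0.6–1.2 and a log difference equal to the log SD, both assumed), the two-stage rule has 79% power with the corrected pre-test and 72–75% with the uncorrected one. A fixed t-test on the log scale has 81%.

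**The case against.** The strongest defence is that the rule does little harm. The Wilcoxon test is named in advance, is valid for an ordinal score, and roughly meets the stated 80% power at one-sided .05. If the pre-test nearly always leads there, the analysis is in effect fixed. That stands as far as validity and power go. It does not stand for reproducibility: the branch is near-certain only under particular choices of summary and critical value, and the plan makes neither. It also does not supply an estimate in SCARF points.

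A second defence is that SCARF may be meant as categorical and so never meets the pre-test. The text does not say so, and chi-squared or Fisher's test would not give a difference to set against the margin either.

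A reader might infer more than the documents support:

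- **That the rule costs SCARF 3–5 points of power.** This appears for roughly symmetric scores. For skewed scores Wilcoxon gains about 3–7 points. The plan gives an SD but no mean or shape, so the sign is unknown.
- **That N = 34 assumed a t-test which the rule then discards.** No test is named, and a Wilcoxon calculation reproduces 34 exactly.
- **That rejection is near-certain whatever the data look like.** Averaging over days or using uncorrected critical values removes that.
- **That power is well short of 80% because of the pre-test.** If alpha is two-sided, power at 34 is about 73% by t-test and 71% by Wilcoxon. That shortfall comes mainly from sidedness.

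**Conclusion.** The concern holds in a limited form. For a one-day score or a per-patient median, the corrected pre-test is settled by the integer scale and carries almost no information about which test is suitable. For other reasonable readings of section IV.F the branch can go either way, so two analysts following the plan faithfully could run different primary tests. In about one trial in 11 to one in 33 (9% to 3%) they would report opposite non-inferiority verdicts. The usual branch gives a valid p-value but, as written, nothing in the units of the margin.

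Neither an inflated error rate nor a general loss of power is shown. The point is worth acting on because the trial is unblinded and the remedy is cheap, not because the planned test is unsound. The figures rest on 17 per arm, no dropout and illustrative 0–4 distributions with SD mostly near 1.1. The narcotic figures rest on assumed lognormal data.

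**What to change.** Delete the normality pre-test for the two primary outcomes.

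For SCARF, state in advance:

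- one per-patient summary of the daily readings;
- one between-arm analysis that gives a difference in SCARF points, with a confidence interval of stated sidedness held against the one-point margin;
- the other method as a sensitivity analysis.

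A Welch interval for the mean difference would serve. If the median wording of the margin is kept, a Hodges-Lehmann interval is the alternative. On whole-number scores its limits are themselves whole numbers, so the plan should say that the upper limit must lie strictly below one.

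For narcotic use, likewise name one analysis. A log-scale analysis is an option, but under the assumed data it gains only about 2 points (81% against 79%) over the two-stage rule with the corrected pre-test. A log(1 + dose) transform depends on the dose unit, and the plan gives no narcotic margin to hold a ratio against.

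The cost is a few sentences, with no extra patients, visits or data. The downside is that using means requires the margin to be restated from a median to a mean difference, and some power may be lost if scores are strongly skewed: 75–76% against 82–83% in the most skewed shape above.
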